APPENDIX I. Secondary Study Questions

Study Theme	Question
Overarching Question	What are the key determinants at service delivery, provider and client levels that influence the uptake of post-pregnancy family planning in the public and private health care sectors in Indonesia and Kenya?
Programmatic Effort	
 • What programmatic inputs increase a woman's likelihood of accepting an FP method immediately postpartum or postabortion? • What are the costs associated with implementing such interventions? • What are the costs and programmatic efforts needed to scale up and sustain these interventions? • What are the barriers and facilitators for young women's accessing post-pregnancy FP services? • What are effective programmatic approaches to engaging the private sector to provide a full range of post-pregnancy family planning methods?
Feasibility	
 • What proportion of post-pregnancy women receive an FP method, according to standard, prior to discharge, among those who opted for an FP method, by age, type of client, timing and method? • To what extent was the health care system able to offer a full range of post-pregnancy FP methods within existing service delivery platforms? (Areas to be examined will include infection prevention, resources, practices, knowledge and skills, commodity supply chain management, labor and delivery staffing, workflow, etc.) • To what extent were the health care facilities offering appropriate and quality post-pregnancy FP counseling at all relevant time points (antenatal care, early labor, prior to discharge, follow-up visits)? • To what extent were providers able to provide, with technical quality, FP counseling and services within the immediate post-pregnancy period? • What are internal and external inputs that incentivize or disincentivize private sector facilities in the provision of post-pregnancy FP services?
Acceptability	
 • What proportion of women post-pregnancy choose a FP method after FP counseling? What proportion receive the method in the immediate post-pregnancy period prior to pre-discharge? • What proportion of women received a different FP method in the immediate post-pregnancy period than the one they opted for prior to delivery or uterine evacuation? What were the determining factors in this difference? • To what extent do providers and women understand the benefits of FP in the immediate post-pregnancy period? • To what extent do providers accept the need to provide post-pregnancy FP counseling and service provision? • What was the continuation rate (within six months post-pregnancy) and reasons for discontinuation for those no longer using the method? • What proportion of women using the lactational amenorrhea method (LAM) transition to another contraceptive method by six months postpartum? To what methods?
Safety	
 • What were the rates of minor, moderate and major adverse events? • Were women experiencing adverse events treated to standard?
Scalability	
 • When scaling up post-pregnancy interventions, what are the key players and what are the key factors? What works and what doesn't? Are these different between public and private sector? • What contributes to the success of implementing and scaling up of post-pregnancy FP in the private sector?

A set of questions on private sector including behavioral economics may also be included based on the interventions/defined intervention package described in Objective 2.
	

APPENDIX II. Timeline of Study Activities

Month 0-3: Completion of Study Tools and IRB	
 1. Completion of Protocol 2. Completion of the following tools: 
 a. Client Interview questionnaires b. Focus Group Discussion and In-Depth Interview guides c. Key Informant Interview guides d. Facility Assessment guide e. Data Abstraction guides f. Data Collector's Field Guide 3. Completion of the following trainings/capacity building tools 
 a. Trainings on FP Counseling and full method mix service provision b. Leadership and Management training and support materials c. Supportive Supervision guides 4. Formation of Technical Advisory Groups 5. Private Sector Formative Assessments 6. Submission of IRB materials
Months 4-6: Site and Study Preparation	
 1. Kenya Intervention and Intervention Implementation Site Preparation: 
 a. Trainings on FP Counseling and full method mix service provision for post-pregnancy FP for public and private facilities b. Leadership and Management support training and intervention for public and private facilities c. Private sector business planning 2. Indonesia Intervention and Intervention Implementation Site Preparation: 
 a. Supportive Supervision on FP Counseling and full method mix service provision for post-pregnancy FP for public and private facilities b. Leadership and Management support training and intervention for public and private facilities c. Private sector business planning 3. Study Preparation: 
 a. Key Informant Interviews 
 i. Ministry of Health and Policy Makers ii. Community Influencers iii. Public Facility providers and management iv. Private Facility providers and management b. First facility assessment (baseline) c. Study Tools testing d. Training materials testing and revisions
Months 6-30: Study Recruitment and follow-up	
 1. Recruitment at Intervention and Control sites 
 a. Client interviews b. Postpartum Client Focus Group Discussions c. Postabortion Client In-Depth Interviews d. Last recruitment by month 24 2. Intervention continuation activities 
 a. Midline and End-line Facility Assessments b. Routine Data Abstraction c. Supportive Supervision/Quality Assurance with Refresher Trainings as needed 3. Regular Technical Advisory Group and Private Sector Associations meetings 4. End-line Key Informant Interviews

	
5. Study analysis activities
 
 1. Control Sites and Control Implementation Sites Trainings 
 e. Kenya: 
 i. Trainings on FP Counseling and full method mix service provision for post-pregnancy FP for public and private facilities ii. Leadership and Management support training and intervention for public and private facilities iii. Private sector business planning f. Indonesia: 
 i. Trainings on FP Counseling and full method mix service provision for post-pregnancy FP for public and private facilities ii. Leadership and Management support training and intervention for public and private facilities iii. Private sector business planning 4. Completion of all Analysis 5. Dissemination of Results
Months 31-36: Phase II Implementation, Analysis, Global Dissemination

Postpregnancy Family Planning Choices in Public and Private Sectors in Kenya and Indonesia (PPFP Choices)

Statistical Analysis Plan

Jhpiego

Unique Protocol ID: IRB00007462

October 31, 2017

Uploaded to Clinicaltrials.gov on November 2, 2017

Data Analysis Plan

Postpregnancy Family Planning Choices in Public and Private Sectors in Kenya and Indonesia (PPFP Choices)

The data analysis plan describes how data collected through different methods will be analyzed after cleaning in order to answer the research questions. Overall, triangulation of findings from quantitative and qualitative data analysis will be done to ensure that the findings provide deeper insights into the study objectives.

- A. **Client Interviews Data Analysis:** Descriptive statistics will be done, computing means and standard deviations for continuous variables and percentages for categorical variables: Proportion of pregnant/postpartum women who choose a FP method during antenatal care (ANC) or early labor, and, of those, what proportion received the FP method in the immediate postpregnancy period (prior to discharge). In addition, logistic **bivariate and multivariable regression** will be used to explore differences in acceptance of PPFP between the intervention and control facilities, A p-value of <0.05 will be considered statistically significant in bivariate analysis for variables to be selected for inclusion in **multilevel analysis** model to determine the factors affecting intention to use and receipt of PPFP.
- B. **Key Informant interviews, Focus Group Discussions and In-Depth Interviews:** Data will all be analyzed using **Grounded Theory methods**. Initial KII, FGD and IDI responses will be translated, transcribed, coded, and analyzed using software to facilitate data management. Quality of translation will be checked for each (KIIs, FGDs and IDIs) through back translation of a randomly-selected subset of 6 interviews. Using Atlas.TI analytical software, coding will be used to conceptually name the data and reduce it to manageable units of information that cover broad and general categories. A priori codes will be developed based on the concepts of interest in this research (perception of risk, benefits and beliefs, etc.) and the study aims. As additional KIIs, FGDs and IDIs are conducted, these a priori codes will be complemented by additional codes that reflect themes and concepts that emerge from the data. Codebooks will be developed for the different concepts to facilitate consistency in the coding process. The coded data will be organized into a hierarchy of themes which are then meaningfully linked to each other to show patterns, relationships and explanations. In conjunction with the coding process, memos will be used to develop conceptual categories and themes and to track emerging insights and interpretations].
- C. **Family Planning Facility Registers:** Using FP Facility Register data, the study team will assess trends in service delivery at participating facilities including the total number of ANC clients, the total number of Labor and Delivery clients, total number of postabortion clients, the total number of postpartum family planning acceptors broken into the type of family planning method accepted. Additionally, the study and project teams will monitor facility records for reports of adverse events related to PPFP acceptance.
- D. **Supportive Supervision Records:** Supportive Supervision Records will primarily be used to measure changes in service provision quality according to data collected during the Supportive Supervision. Overall changes in the number/percent of standards met will be calculated through difference in difference analysis. Facility aggregate provider performance information may also be calculated into assessment of facility readiness and overall facility quality.

E. **Facility Audits Data Analysis:** Mapping of facilities will be visually analyzed to provide further understanding of structural issues that may influence perceptions and key behaviors. Aggregated country and district/county data from the baseline audits will be used to inform final program intervention design where possible. Additionally, select data from the client interviews will be combined with key facility level indicators for a **multilevel analysis** of the factors affecting intention to use and receipt of immediate post-pregnancy family planning methods, and to assess the overall success of the program.

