	Sample Size, assuming 30% attrition, 10% refusal	Design Effect (2.5) and Cluster Size Adjusted Sample Size Per Arm	Sample size per arm (80% Public, 20% Private)	Total per Country (2 arms)
Kenya Public	721	2254	1803	4508
Kenya Private			451	
Indonesia Public	686	2144	1715	4288
Indonesia Private			429	

Table 5: Sample Size Calculations, Postabortion

Study Arm	Base sample size of post-abortion clients (per arm – assuming 50% uptake and 40% continuation at 6-months)	Attrition Adjusted Sample Size per arm (estimating 20% attrition)
Kenya Intervention	194	243
Indonesia Intervention	194	243
Total		486

Separate sample sizes have been calculated for Indonesia and Kenya. Estimates aim to measure a difference in the six-month postpartum acceptance of long-acting reversible and permanent methods (LARC+PMs) by postpartum women seeking services at comparison and intervention facilities. Sample size calculations for both countries are based on a 95% two-sided confidence interval with 80% power. The sample size was calculated in two stages. First, we calculated the sample size for simple random sampling. Next, the sample size was adjusted to take into account a design effect of 2.5 in order to adjust for within-cluster correlation and non-response.

In Indonesia, we used an analysis of PPPF utilization from the 2012 Demographic and Health Survey (DHS) and conversations with the My Choice project team (My Choice is a Bill and Melinda Gates Foundation-supported project currently strengthening family planning services at facilities in Indonesia) to estimate a baseline LARC+PM use of approximately 10% at six months postpartum. In Kenya, we analyzed FP method use among a subset of 3,857 women with a child under one year interviewed during the 2014 Kenya DHS to estimate a LARC+PM use rate of 6% at six months postpartum. Sample sizes were calculated to measure a change from 10% to 15% in Indonesia and from 6% to 10% in Kenya at intervention facilities over the course of the study. We have further estimated a need for 20% of the sample to be recruited from private facilities in order to effectively measure changes in both types of facilities. An overview of the sample size for each country is shown in Table 4. This table displays the required number of post-pregnancy women to be recruited per arm to measure the change in LARC+PM use post-pregnancy from 10% to 15% in Indonesia and from 6% to 10% in Kenya at the end of the study.

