The population of women who will experience postabortion care was calculated differently. Since the current proportion of these women who take up an FP method after PAC has not been reliably determined in the two countries, we have assumed an estimate of 50% (assumption of 50% provides us a high sample size). After six months, we estimate that 40% of them will still be using the method, and thus we need a sample size of 243 women in the intervention group only, per country. This group will be recruited at baseline, and will include an adjustment of 20% to account for loss to follow-up. This sample size is adequate to detect a 10 percentage point change within a 95% two-sided confidence interval at 80% power. The research question for PAC clients is: what percentage of PAC clients who want to use a method of family planning are using a method six months after the premature end of pregnancy? With this question, we hypothesize that 80% who want a method will get a method.

Health Facility Assessments: Prior to implementation of the study, in order to reach adequate sample size, 18 facilities in Kenya (9 intervention and 9 control, which are each split into 5 public and 4 private-for-profit in each arm) and 8 facilities in Indonesia (4 intervention and 4 control, which are each split into 3 public and 1 private-for-profit in each arm) will be purposefully selected in collaboration with respective Ministries of Health.

IV. Participants:

Describe the study participants and the population from which they will be drawn. Specify the inclusion and exclusion criteria. If you plan to include children, note their ages and whether you will include children in foster care. Note if the participants are particularly vulnerable in terms of cognitive limitations, education, legal migration status, incarceration, poverty, or some combination of factors.

Participants will be selected based on their relationship to intervention and control facilities where the PPPF Choices project is being introduced.

Participants in this study fall into two distinct categories: 1) Key Informants, and 2) female clients who participate in Client Interviews, Focus Group Discussions, and In-Depth Interviews.

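### The SAP gives the intervention-control comparison to logistic regression with no stated allowance for facility clustering, and neither document says which model supplies the arm result

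*SAP*

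**What the plan says.** - **Arms.** Protocol III.A and V.C.5.A define the arms as facilities inside an intervention area and a control area, by county in Kenya and district in Indonesia. Assignment is not random.
- **Sizing.** Protocol III.B sizes the study on six-month postpartum use of long-acting and permanent methods (LARC+PM), compared between arms: 6% v 10% in Kenya and 10% v 15% in Indonesia. "Sample size calculations for both countries are based on a 95% two-sided confidence interval with 80% power". The sample is then adjusted for "a design effect of 2.5 in order to adjust for within-cluster correlation and non-response".
- **SAP A.** Bivariate and multivariable logistic regression "will be used to explore differences in acceptance of PPFP between the intervention and control facilities". The text runs straight on: "A p-value of <0.05 will be considered statistically significant in bivariate analysis for variables to be selected for inclusion in" a multilevel model, whose stated purpose is to find factors affecting intention to use and receipt of PPFP.
- **SAP E.** Client and facility data are combined in a multilevel model. Its stated scope is a study "of the factors affecting intention to use and receipt of immediate post-pregnancy family planning methods, and to assess the overall success of the program".
- **Protocol V.C.4.** Regression for the arm comparison is optional and its type is not given. The multilevel analysis is described for determinants only. All outcomes in the study tools are to be reported.
- **Facility counts.** Protocol III.B has 9 facilities per arm in Kenya (5 public, 4 private) and 4 in Indonesia (3 public, 1 private). Protocol V.C.5.A has six in Kenya and four in Indonesia, and a note there leaves the number of implementation sites to be determined.

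**The concern.** The sample size treats women at the same facility as correlated. The only analysis explicitly assigned to the arm comparison does not say that it does so. No random effect, GEE, cluster-robust standard error or small-sample correction is mentioned for it. A reader can find three candidates for the arm p-value (bivariate logistic, multivariable logistic, multilevel), and nothing chooses among them. The SAP also never names six-month LARC+PM use, the outcome that set the sample size, for an arm test.

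The covariate rule adds a second problem. In a non-randomised comparison, a variable that misses p<0.05 on its own can still confound the arm effect, so the screen can remove variables that adjustment needs. If arm is screened like any other variable, it too could drop out; the SAP does not say.

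At stake is whether a programme with no effect could be reported as working well above the nominal rate, and whether the analysis is chosen after the results are seen.

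**Working it through.** **1. The plan's own figure (Protocol Table 4).** n per arm = [1.96√(2p̄q̄) + 0.8416√(p₁q₁ + p₂q₂)]² / (p₂ − p₁)².
- Kenya, 6% v 10%: 720.9, stated 721. Indonesia, 10% v 15%: 685.6, stated 686.
- Times 2.5: 1802.5 and 1715 (public cells 1803 and 1715). Divided by 0.80: 2253.1 and 2143.75, stated 2254 and 2144.

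The last factor, 1/0.80 = 1.25, matches the 80/20 public/private split and is not read as clustering. The 721 and 686 contain no inflation for the 30% attrition and 10% refusal in the column heading; 721/(0.7 × 0.9) would be about 1144. Whether 2.5 is meant to absorb that loss is therefore unclear.

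**2. Implied ICC.** The documents give none. Spread the sample evenly within sector (an assumption). Size-weighted mean facility size is then (5 × 360.6² + 4 × 112.75²)/2254 = 311 in Kenya, and (3 × 571.7² + 1 × 429²)/2144 = 543 in Indonesia. ICC = (2.5 − 1)/(m − 1) = 0.0048 and 0.0028. These are small; a larger ICC would raise every error rate below.

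**3. Type I error of a single-level test.** α* = 2[1 − Φ(1.96/√DE)], two-sided 5%. The level comes from Protocol III.B, because the SAP sets none for the arm test.

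| Assumption | DE | α* |
|---|---|---|
| 2.5 applies to the analysed data | 2.5 | 21.5% |
| ICC from step 2 held, 63% analysed (0.7 × 0.9) | 1 + (0.63m − 1) × ICC = 1.94 | 16% |
| 2.5 also absorbs 30% attrition (2.5 × 0.7) | 1.75 | 13.8% |
| 2.5 also absorbs attrition and refusal (2.5 × 0.7 × 0.9) | 1.575 | 11.8% |

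Beta-binomial simulation with no arm effect at 2.5 gave 21.2-21.7% for the single-level test and 4.8-5.1% for a facility-level t-test.

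**4. Would a random effect be enough?** In two simulations for Indonesia at 2.5, a maximum-likelihood random-effects model with a Wald z test rejected in 13.7% and 14.5% of null trials, against 21.6% and 22.6% single-level. REML with z gave 9.0% and 9.6%. Four facilities per arm therefore also need small-sample inference.

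**5. Interval width.** Degrees of freedom with arm and sector fitted: 18 − 3 = 15 in Kenya (12 − 3 = 9 at six per arm) and 8 − 3 = 5 in Indonesia. Ratio to a single-level interval = √DE × t(0.975, df)/1.96. At 2.5 this is 1.581 × 2.131/1.96 = 1.72 in Kenya (1.82 with 9 df) and 1.581 × 2.571/1.96 = 2.07 in Indonesia.

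**6. Power of a correct test.** Noncentral t with ncp = (p₂ − p₁)/√[(p₁q₁ + p₂q₂) × DE/N].

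| Analysed | DE | ncp | Kenya, 15 df | Indonesia, 5 df |
|---|---|---|---|---|
| All | 2.5 | 3.14 | 83% | 71% |
| 70%, ICC held | 2.05 | 2.90 | 77% | 64% |
| 63%, ICC held | 1.94 | 2.83 | 75% | 62% |
| 70%, 2.5 held | 2.5 | 2.63 | 69% | 56% |
| 63%, 2.5 held | 2.5 | 2.49 | 64% | 52% |

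With six facilities per arm in Kenya (9 df), all analysed and 2.5 held, power is about 80%.

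**The case against.** The strongest reply is that the SAP does contain a multilevel model. The logistic sentence in SAP A runs on into the screen for that model, so the section can be read as one sequence: bivariate, multivariable, then multilevel. Receipt of PPFP overlaps with acceptance, and Appendix I asks which programme inputs raise acceptance, so arm would be a natural facility-level term. SAP E points the same way. This reply stands in part. A reader might infer that the SAP plans an unclustered arm test, and the documents do not support that; they leave the matter open. But neither section names an arm term, an outcome or a test, so the multilevel text adds a candidate without settling which one is used. Step 4 also shows that, with few facilities, a random effect alone would not restore the 5% level.

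A reader might also infer that real power is only 64% and 52%. That holds only if 2.5 was meant for the analysed sample and 63% of it is analysed. Protocol Tables 3 and 4 count women recruited or to be recruited, so refusers may already be excluded and 70% may be the better figure. If the ICC is fixed instead, the design effect falls as facilities shrink.

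The protocol does say that all outcomes will be reported, which would include six-month use. That is general reporting and not a specified arm test.

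Finally, the arm comparison is described as exploratory, and Protocol I lists programme impact among the secondary questions. That limits the weight of the point but does not remove it.

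**Conclusion.** The point holds as an omission and should be fixed. The SAP's only explicit arm analysis carries no stated allowance for clustering, and the documents do not say which model gives the arm result.

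The error rates are conditional on a single-level fit: about 21.5% if the design effect in the analysed data is 2.5, about 16% if the full-enrolment ICC applies and 63% are analysed, and about 12-14% if 2.5 also absorbs non-response. They assume that the same design effect applies to PPFP acceptance as to LARC+PM use. The degrees of freedom rest on facility counts that the protocol states inconsistently for Kenya.

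The p<0.05 screen is a weakness whichever model is used. None of this bears on the primary question about determinants; it concerns the comparison on which the postpartum sample was sized.

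**What to change.** In SAP A:
- Name one clustered arm analysis per country, for six-month LARC+PM use and for PPFP acceptance. Use either a facility-level analysis or a facility random-intercept logistic model, with small-sample inference on between-facility degrees of freedom.
- Force arm into the model. Replace the p<0.05 screen with a short prespecified list: sector plus sociodemographic items already collected.
- State how the SAP E multilevel analysis relates to this test.
- Reconcile the facility counts (Kenya 9 or 6 per arm, and the sites still to be determined), because the degrees of freedom depend on them.
- State that area remains confounded with arm, since each country has one intervention area and one control area.

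The cost is SAP wording and modest extra analysis, with no new data. The price is wider intervals and the lower power in step 6, which should be reported openly. The change deals with facility clustering only; no wording can separate the programme from a difference between the two areas.

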XII. Please complete the attached worksheet of your Logic Model and submit to Jhpiego IRBhelp with your completed research protocol. *This is for Jhpiego internal review only.*

COMPLETE THE FOLLOWING SECTIONS WHEN RELEVANT TO YOUR STUDY:

XIII. Secondary Data Analysis of Existing Data:

A. Study Design:

1. Describe your study design and methods. The study design must relate to your stated aims/objectives.

In addition to the methods described above, the study will monitor immediate postpregnancy family planning clients and participating providers and facilities through analysis of routine program and facility records. These records are outlined below.

FP Facility Register	Facility clients	Determine overall facility PPFP acceptance, PPFP method mix and adverse events	Monthly service statistic record review	Descriptive statistics
Supportive Supervision Records	Kenya: Intervention Site Providers Indonesia: All providers	Measure service quality against PPFP performance standards	Intervention Area: Kenya: 3 and 12 months post-training Indonesia: Beginning of the study, Year 2, Year 3 Control Area: Kenya and Indonesia: month 30	Descriptive, chi-sq, ANOVA (depending on sample size)

Family Planning Facility Registers: Information about immediate PPFP clients will be documented in a Family Planning register at the intervention and control health facility where they receive care – part of the health system. This information will be used to track overall PPFP service statistics, assist with validating responses from the Client Interviews, and help the study team ensure that the Client Interview sample continues to be representative of the overall client population (especially regarding adolescent enrollment).

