Supportive Supervision Records: The project will employ Jhpiego staff and a ministry of health representative or consultant to provide Supportive Supervision to intervention facility providers trained in implant service provision and counseling at project facilities. Supportive Supervision is a proven method for improving the quality of services offered by trained providers through guiding, helping, and encouraging staff to continue using the skills they learn through training. Regular Supportive Supervision visits will be conducted to each facility. During these visits, supervisors use a Supportive Supervision Checklist to monitor the quality of services provided. Quality will be measured against a set of performance standards developed at the national level with stakeholders from each country. The study team will use

Supportive Supervision Records to track whether or not services are improving at project facilities. Data will be linked to facilities to assess overall facility quality and help determine the impact of the intervention.

2. Provide an estimated sample size and an explanation for that number.

Family Planning Facility Registers: We estimate that roughly 15% of women who deliver at intervention facilities and 10% of women who deliver at control facilities will accept a method of postpartum family planning and that on average 30 women per month will deliver in each of the 62 project facilities over the course of the project. Therefore, we anticipate facilities will collect information about approximately 3,906 postpartum FP acceptor clients during the 30 months of the study. Furthermore, we estimate that approximately 50% of women receiving postabortion care at both intervention and control facilities will accept a method of postabortion family planning and that on average 12 women per month will receive PAC at the project facilities over the course of the project. Therefore, we anticipate facilities will collect information about approximately 4,680 postabortion FP acceptor clients during the 30 months of the study. Based on these estimates, we expect to collect de-identified service statistics for approximately **8,586 postpregnancy FP acceptor clients**.

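### The planned difference-in-difference on supervision standards cannot be estimated: the schedule gives control facilities one score, and Kenya has no pre-training score in either area

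*SAP*

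**What the plan says.** SAP section D (Supportive Supervision Records) and Protocol XIII.A.3 carry the same sentence: "Overall changes in the number/percent of standards met will be calculated through difference in difference analysis". Neither names the groups to be compared or the times between which change is measured. The narrative in Protocol XIII.A.1 says the scores will be linked to facilities and used in judging whether the intervention had an effect. That points to intervention area versus control area.

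The only dated scoring schedule is the Supportive Supervision row of the records table in Protocol XIII.A.1:

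- Intervention area: "Kenya: 3 and 12 months post-training" and "Indonesia: Beginning of the study, Year 2, Year 3".
- Control area: "Control Area: Kenya and Indonesia: month 30".
- Analysis column: "Descriptive, chi-sq, ANOVA (depending on sample size", with no mention of difference-in-difference.

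The documents also disagree on who is scored. The table row gives "Kenya: Intervention Site Providers" as the Kenyan sample, yet it schedules a Kenyan control score. The narrative speaks of staff who "provide Supportive Supervision to intervention facility providers trained in implant service provision and counseling at project facilities", then adds "Regular Supportive Supervision visits will be conducted to each facility" without dates. XIII.A.2 extends supervision to all participating facilities and counts 200 + 100 = 300 providers from both arms. XIII.B.1 describes only providers at intervention facilities.

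**The concern.** A difference-in-difference subtracts the control group's change from the intervention group's change. A control area scored once has no change to subtract, and more providers or a different model cannot supply it.

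This matters because the areas are chosen with the ministries of health and are not randomised (Protocol V.C.5.A). Adjusting for where each area started is what would let these records support a statement about the programme's effect on service quality. If that contrast cannot be computed, the analyst must settle on another one once the data are in. Each contrast the schedule allows leaves in something the difference-in-difference would have removed: the baseline gap between areas, or the time trend.

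**Working it through.** The documents state no sample size, power or effect for this analysis, so there is no figure to reproduce. The check is whether the scheduled scores identify the contrast.

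**Inputs (records table, Protocol XIII.A.1).** Here, before and after refer to the start of the programme in the intervention area.

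| Country, area | Before | After |
|---|---|---|
| Indonesia, intervention | beginning of study | Year 2, Year 3 |
| Indonesia, control | none | month 30 |
| Kenya, intervention | none | 3 and 12 months post-training |
| Kenya, control | none | month 30 |

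**Model.** Score = b0 + b1·area + b2·after + b3·(area × after), where b3 is the difference-in-difference. It has four parameters.

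**Indonesia.** The filled cells give b0 + b1 (intervention before), b0 + b1 + b2 + b3 (intervention after) and b0 + b2 (control after).
- Intervention after minus before = b2 + b3, so the time trend remains.
- Intervention after minus control after = b1 + b3, so the baseline gap remains.
- The rank is 3 of 4, and b3 cannot be isolated.

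**Kenya.** The filled cells give b0 + b1 + b2 + b3 and b0 + b2. The only difference available is b1 + b3. The rank is 2 of 4, and b3 is not estimable.

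**Variants tried.**
- Treating Kenya's 3-month score as before: rank 3 of 4, not estimable.
- Indonesia with time at three levels (6 parameters, 4 filled cells): rank 4, Year 3 interaction not estimable.
- Area and calendar-time effects: Kenya rank 3 of 5, Indonesia 4 of 5, neither estimable.
- An ANOVA group-by-time term meets the same empty control cell.

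**What would restore it.**
- Indonesia with a control before score: rank 4 of 4, estimable. Minimum missing: 1.
- Kenya with a control before score only: rank 3 of 4, still not estimable. The same holds with an intervention before score only.
- Kenya with both: rank 4 of 4, estimable. Minimum missing: 2.

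**Size of the error in an after-only comparison.** By identity, (intervention after − control after) = difference-in-difference + (intervention before − control before). An assumed baseline gap of 5 to 15 percentage points of standards met shifts the result by 5 to 15 points.

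**Timing.** Assume Kenyan training falls in months 4-6 (Appendix II; the records table does not say which training starts the clock).
- The 3-month scores fall at 4 + 3 = 7 to 6 + 3 = 9 months.
- The 12-month scores fall at 4 + 12 = 16 to 6 + 12 = 18 months.
- The gap to the control score is 30 − 18 = 12 to 30 − 16 = 14 months.

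In Indonesia, with Year 3 taken as months 25-36, the gap to month 30 is at most 36 − 30 = 6 months.

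**The case against.** The strongest answer is that non-estimability depends on two readings.

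**The comparison groups are not named.** The study also contrasts public with private facilities, and a public-private difference-in-difference within the intervention area could be computed from the scheduled times (three in Indonesia, two in Kenya). This is true, but such a contrast would not serve the stated use of these records in judging the intervention's impact. If it was intended, the SAP needs to say so.

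**The dated list may not be complete.** The protocol promises regular visits to each facility and supervision at all participating facilities, so control scores could exist outside the table. Month 30 might also be a date for reviewing records rather than for scoring, since the neighbouring register row describes a record review. This keeps some force. However, those visits are undated, other sentences confine supervision to intervention facilities, and the times after training read as scoring times. Appendix II lists supervision in months 6-30 under intervention continuation, but that is weak evidence either way, because the same heading covers activities run in both arms.

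**Other quality data exist.** Facility audits run at baseline, midline and endline, and the protocol mentions provider quality assessments. The audits cover records, staffing and commodities. Neither source is described as supplying the standards-met scores from supervision.

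**Methods are already named.** The table row lists families of test, so the analyst is not wholly free. It does not say which groups or times are contrasted.

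It is also fair that the 5 to 15 point gap is illustrative and that this is a secondary measure.

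**Conclusion.** The concern holds. On the schedule as written, a difference-in-difference between intervention and control areas is not identified in either country: one score is missing in Indonesia and two in Kenya. The conclusion assumes that the areas are the groups meant and that the records table lists all the scores. The documents favour both readings but do not state them. That an after-only contrast absorbs the baseline gap is exact; the size of that gap and the 12 to 14 month Kenyan time difference rest on the assumptions given. The point should be fixed, but its reach is limited to this process measure.

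**What to change.** Reconcile the records table in Protocol XIII.A.1, sections XIII.A.2, XIII.A.3 and XIII.B.1, and SAP section D on who is scored, when, which groups are compared and by what method. In particular, state whether Kenyan control providers are scored. Then replace the difference-in-difference sentence with what the schedule supports:

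1. **Indonesia:** change within the intervention area from the beginning of the study to Year 3, plus intervention Year 3 versus control month 30, labelled as not baseline-adjusted. State whether the first score precedes the start of supervision, because Appendix II makes supervision part of the intervention there.
2. **Kenya:** the 3-to-12-month change in the intervention area, labelled a post-training trend. Any comparison with the control score at month 30 is descriptive only, with the time gap and the missing baseline stated.
3. **Both:** a statement that none of these contrasts alone estimates the programme effect.

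These changes cost wording only.

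Keeping the difference-in-difference costs more. It needs comparable scores from before the intervention area's programme starts: one control-area round in Indonesia and one round covering both areas in Kenya, plus one further Kenyan area score if the after times are to match. This is possible only if such scores already exist or the programme has not begun, and the documents do not say which. A score taken merely before the control area's own training does not help: month 30 already precedes that training, which Appendix II places in months 31-36.
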